4.4 Excluded Therapies

Subjects should not be enrolled in the study if they are currently (defined as 2 weeks prior to and at the screening visit) taking any of the following agents listed below:

1. GLP-1 receptor agonists (e.g., Byetta®, Bydureon®, Adlyxin®, Victoza®, Saxenda®, Trulicity®, Tanzeum®, Ozempic®)
2. Amylin analogs (e.g., Symlin®)
3. Thiazolidinediones (e.g., Actos®, Avandia®)
4. Any combination medications that contain 1-4 above (e.g., Avandamet®, Avandaryl®, Duetact®, Actoplus Met®, PioMet®)
5. Oral and injectable antibiotics
6. Oral or injectable corticosteroids (e.g., prednisone)
7. Chemotherapy
8. Opioids
9. Probiotics
10. Radiation
11. Cytotoxic therapy

12. Immune suppressants
13. Antiepileptic drugs
14. Colesevelam (Welchol®)
15. Acarbose (Glucobay®)
16. Miglitol (Glyset®)
17. Over-the-counter products that contain ephedrine
18. Other supplements containing butyrate
19. Medications that alter gastrointestinal motility including but not limited to metoclopramide (Reglan®), Metamucil® or other bulk fiber agents, emollient agents like ducosate, stimulants like Dulcolax® or castor oil, magnesium hydroxide (Milk of Magnesia®), hyperosmolar preparations (lactulose, sorbitol, MiraLAX®), opioids (e.g., Vicodin®, codeine, Percocet®), Adsorbents (Immodium®, Kaopectate®, Pepto-Bismol®), or anti-emetics (e.g., Zofran®, Kytril®, Compazine®, Phenergan®)

If a subject requires any of the above agents during the study, he/she should contact the study team to determine if there is an alternative available.

5. INVESTIGATIONAL PRODUCT

5.1 Investigational Product Description and Packaging

BKR-017 is a proprietary oral tablet formulation designed to target delivery of butyrate to the colon and provide sustained-release as the tablet passes through the colon. [REDACTED]

[REDACTED]

[REDACTED]

[REDACTED] [REDACTED] [REDACTED]

BioKier will arrange for the shipment of tablets directly from the manufacturer to the Mayo Clinic pharmacy in 150-ml HDPE white bottles (54 tablets per bottle). Each bottle contains enough test product for one week of dosing (plus 2 extra days). Each bottle will be labeled with the following information:

Study ID: CL-301

Investigator: [name]
Mayo Clinic, Rochester, MN

Take 3 tablets before breakfast and 3 tablets before bedtime daily

Keep at room temperature

Investigational use only

Bottle contains 54 tablets of BKR-017

Subject Number: _____ **Bottle Number:** _____

5.2 Investigational Product Storage, Dispensing, and Return

Bottles containing test product (BKR-017 tablets) will be stored at room temperature at the Mayo Clinic Research Pharmacy.

The Research Pharmacist will keep detailed records of dispensation and return.

During Test Period

At Visit 1 (Day -28), eligible subjects will be given an 8-week supply of test product. Subjects will be instructed to begin dosing on Day 0. Additionally, Subjects will be instructed to complete the diary card daily and to return the diary card (with insulin usage, dosing information, changes in medications, and any adverse events) every 7 to 10 days by mail/email to the study team.

.

At Visit 2 (Day 48), the study CGM sensor, will be returned as well as all unused tablets in the original container(s). Diary cards will be reviewed and reconciled with the number of tablets returned. Subjects will be questioned about any missed doses based on the number of tablets returned, and the information supplied will be documented in the subject's study records.

5.3 Investigational Product Administration

The tablets will be self-administered orally twice daily; the first daily dose before breakfast, and the second daily dose before bedtime.

If the first daily dose is not administered before breakfast, it can be administered up to 12:00, noon. However, if the first daily dose is not taken by 12:00, noon it will be considered a missed dose; the bedtime dose should be taken as scheduled even if the morning dose was taken late or missed. If an evening dose is not taken by midnight, it will be considered a missed dose. All missed doses should be recorded on the diary card and returned in the original container at the next visit.

The study staff will counsel subjects who repeatedly miss doses about the importance of being compliant with the dosing regimen. However, if the investigator determines that a subject is not willing or able to reasonably comply with the dosing regimen, the subject should be discontinued.

5.4 Per Protocol Population

If a subject misses 15% of the required 96 doses (i.e., 14 or more doses) during the test period, then data from that subject will be excluded from the per-protocol efficacy assessment and included only in the intent-to-treat (ITT) analysis.

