2. STUDY PURPOSE AND OBJECTIVES

This study will test the hypothesis that delivery of the butyrate-containing BKR-017 tablet to the colon of T1D subjects will improve insulin sensitivity. Additionally, the effect of BKR-017 on triglycerides and glucose variability will be assessed. The safety and tolerability of repeat dosing (up to 48 days of administration) of BKR-017 will be determined. By exploration of the effects of BKR-017 on various metabolic biomarkers, the data generated from this study will be used to support continued evaluations of BKR-017 as non-prescription product for T1D patients requiring

nutritional support to improve cardiometabolic health. Furthermore, these data will support continued evaluation of BKR-017 for the regulation of weight and hypertriglyceridemia.

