4.3 Inclusion/Exclusion Criteria

Inclusion Criteria:

1. Males and females between the ages of 20 and 80 years at the time of screening, inclusive
2. Diagnosed with T1D and under the care of a healthcare professional for its management
3. HbA1c 6.4-8.9%, inclusive
4. Has given written informed consent to participate in this study
5. Willing to complete 28-day baseline period and 48 -day test period
6. Willing to maintain current diet and exercise routine for the duration of the study
7. Current use of a Dexcom Continuous Glucose Monitor (CGM)

Exclusion Criteria:

1. History of bariatric or intestinal surgery
2. Active gastrointestinal disease including but not limited to irritable bowel syndrome, inflammatory bowel disease (e.g., Crohn's disease and ulcerative colitis), diverticulitis, gastroparesis, or chronic/frequent diarrhea or chronic/frequent constipation

3. Active and clinically significant hepatic, pancreatic disease, or renal disease as determined by the investigator
4. History of significant heart disease, including congestive heart failure, prior MI, chronic atrial or ventricular fibrillation, coronary artery disease, cerebral vascular disease, or other cardiovascular disease, that in the opinion of the investigator should exclude the subject from the study
5. Severely uncontrolled hypertension at screening defined as a systolic blood pressure > 180 mmHg or a diastolic blood pressure > 110 mmHg on the average of two seated measurements after being at rest for at least 5 minutes
6. Uncontrolled hyperthyroidism or hypothyroidism, or other significant thyroid disease
7. Active significant infection as determined by the investigator
8. Known allergy to butyrate or any of the components of the tablets
9. Participation in a clinical trial and/or treatment with an investigational drug during the 30 days before screening, or within 5 half-lives of receipt of an investigational drug or twice the duration of the biological effect of any investigational drug (whichever is longer)
10. Pregnant, nursing, or trying to become pregnant
11. Presence of pitting edema on physical exam
12. High fiber diet
13. In the investigator's judgment, the subject is not suitable for the study for any other reason or cannot commit to the requirements of the study.
14. Subject is taking one or more of the excluded therapies. See list of excluded therapies in section 4.4.

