6.2 Study Periods

The timing and evaluations for all visits to occur within the Baseline and Treatment Periods are defined in this section. Every attempt should be made to have all visits occurred at the required visit day. If, however, the subject is unable to adhere to the required visit day, a visit window of -/+ 2 days is allowed (i.e., 2 days prior or 2 days after the required visit day).

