6.2.2 Termination of Baseline Period, Initiation of Test Period

Day 0, the following will be performed:

1. Subjects will be instructed to administer the first dose of test product prior to their mid-day meal and the second daily dose just prior to bedtime on Day 0.
2. Subjects will be instructed to keep their Dexcom CLARITY app active, so that glucose monitoring data can be accessed by the study team.
3. Subjects will be reminded to mail/email diary cards to the study team every 7 to 10 days. Subjects using an insulin pump, will be advised to mail/email a copy of their pump settings and insulin doses every 7 to 10 days or upload their pump data to a prespecified, linked online account compatible with their pump (i.e. Medtronic CareLink, Tandem T Connect or Glooko), whereby the relevant data can be abstracted by the study team.
4. Subjects will also be instructed not to make any modifications to their diet or exercise routine.
5. Subjects will be scheduled to return to the OPC for Visit 2 and instructed to return all unused tablets in the original container(s) along with any diary cards.

On Day 48 (Visit 2, Final Visit):

1. Subjects will report to the OPC in the morning, before 12:00 noon. If a subject is not able to comply with the Day 0 requirement, a variance of -2 days (or Day 46 or 50) is allowed.
2. Urine pregnancy test will be obtained for females of childbearing potential.
3. Subjects will return all unused tablets in the original container(s) along with any diaries.
4. Blood pressure, height, weight, and waist and hip circumference will be obtained to calculate the WHR. Fasting samples will be obtained for glucose and triglycerides. Additional blood samples will be obtained for HbA1c, routine hematology, routine chemistry assessments CPR, and for exploratory biomarkers hs-CRP and 1,5AG.
5. An abbreviated physical exam will be performed.
6. Study staff will review the subject's diary in order to reconcile tablets returned with any doses missed.

7. Subjects will be questioned about any changes in health status/adverse events and any changes in therapy or medications
8. Study personnel will remove the CGM sensor from the subject's abdomen and download the data to the Dexcom CLARITY data storage location.

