12. ANALYSIS CONVENTIONS

12.1 Analysis Sets

An analysis database of all efficacy data collected will be generated (ITT Population). In addition, an analysis set of all subjects without major protocol violations (per protocol population) will consist of all subjects who took at least 85% of the 96 required doses (i.e., 82 or more doses).

The safety analysis set will include all subjects who received any amount of test product.

Analysis plans are detailed further in a Statistical Analysis Plan document (SAP).

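### Sections 5.4 and 12.1 classify a subject with exactly 14 missed doses in opposite ways, and the fixed cutoff of 82 doses is too strict when Visit 2 is early

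*Combined protocol and SAP*

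**What the plan says.** Two sections define the per-protocol set by adherence.

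- Section 5.4 (Per Protocol Population) gives the exclusion side: "If a subject misses 15% of the required 96 doses (i.e., 14 or more doses) during the test period". Such a subject's data are "excluded from the per-protocol efficacy assessment and included only in the intent-to-treat (ITT) analysis".
- Section 12.1 (Analysis Sets) gives the inclusion side: "all subjects who took at least 85% of the 96 required doses (i.e., 82 or more doses").

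Both sections fix the number of required doses at 96. The passages that determine that number are:

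- Section 5.3: "The tablets will be self-administered orally twice daily".
- Section 6.2.2: on Day 0 subjects are told to "administer the first dose of test product prior to their mid-day meal and the second daily dose just prior to bedtime on Day 0", so Day 0 carries two doses.
- Section 4.3: "Willing to complete 28-day baseline period and 48 -day test period".
- Section 2: "repeat dosing (up to 48 days of administration").
- Section 6.2: "a visit window of -/+ 2 days is allowed". Section 6.2.2 repeats the window for Visit 2, naming Days 46 and 50, and has unused tablets handed back at that visit.

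Section 12.6 has every efficacy analysis, including the primary one on eGDR, run in both the ITT and the per-protocol populations.

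**The concern.** The two sections should be mirror images, and at one value they are not. A subject at that value has no defined per-protocol status, although the paired t-test on eGDR is to be repeated in that set. The planned number of completers is 13 (synopsis and Section 4.1), and Section 11.2 speaks of 12 subjects, so moving one person in or out can matter to the estimate. The study is open-label. If the conflict is found only at analysis, whoever resolves it may already have seen the data.

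The second issue is the fixed denominator. If the permitted window shortens dosing, a cutoff stated as a count no longer corresponds to the 85% it is meant to represent.

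**Working it through.** **Required doses.** Two per day (5.3), two on Day 0 (6.2.2), 48 days (4.3). Days 0 to 47 are 48 dosing days: 2 × 48 = 96. The plan's figure reproduces.

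**Cutoff in 12.1.** 0.85 × 96 = 81.6, rounded up to 82. This reproduces; 82/96 = 85.4%.

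**Cutoff in 5.4.** 0.15 × 96 = 14.4, so the smallest whole number of missed doses that reaches 15% is 15. The stated 14 does not reproduce: 14/96 = 14.6%, below 15%.

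**Both rules on the 96-dose schedule:**

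| Missed | Taken | % missed | % taken | 5.4 count (14 or more out) | 5.4 percentage (15% out) | 12.1 (82 or more in) |
|---|---|---|---|---|---|---|
| 13 | 83 | 13.5 | 86.5 | in | in | in |
| 14 | 82 | 14.6 | 85.4 | **out** | in | **in** |
| 15 | 81 | 15.6 | 84.4 | out | out | out |

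The conflict sits at exactly one value. The two percentages agree for every subject, because exactly 15% missed is not attainable with 96 doses. If 5.4's count is set to 15, the two sections agree everywhere on this schedule.

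**Early Visit 2, Day 46.** With dosing on Days 0 to 45, 2 × 46 = 92 doses are possible (93 with a morning dose on the visit day). No later doses can be taken, because the tablets are returned.

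- 85% of 92 is 78.2, so 79 doses meet 85%.
- A fixed 82 demands 82/92 = 89.1%.
- 79/92 = 85.9%, 80/92 = 87.0% and 81/92 = 88.0% all fail 12.1 although they are at or above 85% of the doses available.
- With 93 possible doses, 85% is 79.05, so 80 are needed; 80 and 81 taken (86.0% and 87.1%) fail.

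**Early Visit 2, Day 47.** 2 × 47 = 94 doses; 85% is 79.9, so 80 are needed. The fixed 82 demands 82/94 = 87.2%; 80 and 81 taken (85.1% and 86.2%) fail.

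**Late Visit 2, Day 49 or 50.** If dosing ends after 48 days, 96 remains right. If it continued to the visit, there would be 98 or 100 doses (2 × 49 or 2 × 50), and 82 would be 82/100 = 82.0% on Day 50. That is an assumption; no section states it.

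**Weight of one subject.** 1/13 = 7.7%; 1/12 = 8.3%.

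**The case against.** The strongest reply is that the practical reach is slight. On the nominal schedule only a subject with exactly 14 missed doses is affected, and the per-protocol analysis repeats an ITT analysis. That is fair and limits the weight of the point, but it does not remove the contradiction.

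Three stronger readings are tempting, and the documents do not carry them.

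- A reader might infer that 96 is wrong whenever the visit window is used. For Day 49 or 50 this requires dosing beyond 48 days. Nothing schedules it, and Section 2, Section 4.3 and the 48-day dosing duration in the synopsis point the other way. The 8-week supply dispensed at Visit 1 makes longer dosing possible but does not prescribe it.
- A reader might infer that the window widens the conflict between the two sections. On Day 46, 79 to 81 taken is 11 to 13 missed out of 92, which passes 5.4's count and fails 12.1. But that counts missed doses against 92, whereas both sections name 96. Against 96 the same subjects have 15 to 17 missed and are out under both rules. On that literal reading the sections still disagree only at 82 taken, and the early visit is a matter of an over-strict cutoff.
- A reader might infer that the choice of rule will be made with results in view. Section 12.1 defers further detail to a statistical analysis plan, which might settle the count. No such resolution appears in the text supplied, so a post hoc choice is possible but not established.

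**Conclusion.** The contradiction holds and needs no assumption: 14 missed, or 82 taken, gives opposite per-protocol status under 5.4 and 12.1. The error lies in 5.4's count, which disagrees with its own percentage; 12.1's 82 follows correctly from 85%.

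The fixed cutoff is also too strict for an early Visit 2. At its largest, on Day 46, it demands 89.1% instead of 85% and wrongly fails 79 to 81 doses taken. This rests on dosing through the day before the visit; with a visit-day morning dose the affected counts are 80 and 81. For a late Visit 2 the required number of doses is not spelled out, but 96 is not shown to be wrong.

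The effect is confined to subjects near the cutoff, each about 8% of a set of 12 or 13. It should be corrected because it is a wrong threshold for a set in which every efficacy analysis is repeated, and the conflict leaves room for a choice after open-label data are seen. It does not threaten the ITT analysis.

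**What to change.** 1. State one rule in both sections: a subject is per-protocol if at least 85% of the doses required of that subject up to Visit 2 were taken. For 96 doses this means 82 or more taken, so exclusion begins at 15 missed.
2. Delete the count of 14 from Section 5.4.
3. When Visit 2 is early, use the doses actually available as the denominator, and say whether a visit-day morning dose counts.
4. Reconcile Sections 2, 6.2 and 6.2.2 so that the required number of doses is defined when Visit 2 is late. How long treatment lasts in that case is for the sponsor and investigator to state; no duration is proposed here.

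The cost is a few sentences in the protocol, carried into the statistical analysis plan, before the data are examined. No additional data are needed.

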6. STUDY PROCEDURES

Table 1: Time & Events Schedule

	Pre-Screen	Baseline Period			Test Period				
		Visit 1							Visit 2
		D -28		D 0	D 18	D 28			D 48
Review of Eligibility & Study Requirements	X								
Written Informed Consent		X							
Review of Inclusion / Exclusion criteria		X							
Medical History & Demographics		X							
Blood Pressure (seated position at the start of visit)		X							X
Body Weight and Waist-to-Hip-Ratio		X							X
Hematology and Chemistry (including CPR)		X							X
Abbreviated Physical Exam		X							X
Urine Pregnancy Test (women of childbearing potential)		X							X
Dispense and/or Review Diaries for Compliance (Insulin and treatment)		X		X		X	X		X
Subject number assigned		X							
CGM sensors dispensed		X							
CGM sensor collected									X
Treatment Dispensed		X							
Fasting Glucose and Triglycerides		X							X
HbA1c		X							X
Exploratory Tests hs-CRP and 1,5AG		X							X
Concomitant Medication Review		X		X		X	X		X
Adverse Event Review				X		X	X		X

6.1 Screening Period

6.1.1 Recruitment and Prequalification

Subjects will be recruited through advertisements and other materials approved by the Mayo Clinic IRB. Potential study subjects interested in participating may also be referred to the research team.

Pre-screening will be performed to determine basic study eligibility information including:

- Age
- Type and age of onset of diabetes; confirmation of T1D diagnosis
- Understanding and willingness to commit to the study requirements
- Concomitant medications, including the need to refrain from use during the study of drugs that alter gastrointestinal motility

Subjects who meet the initial criteria and are willing to participate will be scheduled for a Screening Visit (Visit 1). Subjects will be required to fast (i.e., no food or beverages other than water) for at least 10 hours prior to the screening visit.

6.1.2 Visit 1 (Screening)

The screening visit will take place at the Outpatient Clinic (OPC), as described in Section 6.2.1 below, and include:

- Review of inclusion/exclusion criteria and eligibility
- Subject consent will be obtained; documented with an Informed Consent Form (ICF) signed by subject

6.2 Study Periods

The timing and evaluations for all visits to occur within the Baseline and Treatment Periods are defined in this section. Every attempt should be made to have all visits occurred at the required visit day. If, however, the subject is unable to adhere to the required visit day, a visit window of -/+ 2 days is allowed (i.e., 2 days prior or 2 days after the required visit day).

6.2.1 Baseline Period (Day -28 to Day 0, Visit 1)

The screening visit will take place on Day -28 before midday at the Outpatient Clinic (OPC). The following will be performed:

1. Review of inclusion/exclusion criteria and eligibility
2. Subject consent will be obtained; documented with an Informed Consent Form (ICF) signed by subject. Written informed consent must be obtained before any study procedures are

performed and a record of the subject's consent (i.e., an original, signed and dated consent form) is to be maintained in the study files and a copy provided to the subject.

Subjects whose HbA1c is within the range of 6.4-8.9% and meet all other preliminary eligibility criteria will continue with all other screening procedures, as follows:

1. Urine pregnancy test for females of childbearing potential (exclude if positive and do not continue with other screening assessments).
2. Confirm that the subject is in a fasted state.
3. Obtain blood samples for routine hematology and chemistry tests, including CPR for safety evaluations, plus fasting glucose and triglycerides. See [Tables 3](#) and [4](#), [Appendix 2](#), for safety laboratory evaluations.
4. Demographics (date of birth, gender, race, and ethnicity).
5. Confirm medical history, including HTN determination, and including diabetes classification, onset/diagnosis date of diabetes, diabetes therapy(s), and therapy duration(s).
6. Obtain concomitant therapies (generic name, dose, route, frequency, date started, and reason for use).
7. Obtain vital signs (heart rate and blood pressure) in a seated position.
8. Obtain subject's height and weight
9. Obtain waist and hip circumference to calculate the WHR.
10. Perform standard physical exam including an exam to detect any signs of edema. Any amount of pitting edema will exclude a subject.
11. After signing consent and meeting all inclusion criteria, subjects will be instructed on, and supplied with a study provided Dexcom G6 sensors, to collect glucose data. Subjects will be instructed to keep their Dexcom CLARITY app active, so that glucose monitoring data can be accessed by the study team.
12. Diary cards will be provided for the subject to record insulin doses, changes to concomitant medications and adverse events. Diary cards will be mailed/mailed to the study team every 7 to 10 days. Subjects using an insulin pump, will be advised to mail/email a copy of their pump settings and insulin doses every 7 to 10 days or upload their pump data to a prespecified, linked online account compatible with their pump (i.e. Medtronic CareLink, Tandem T Connect or Glooko), whereby the relevant data can be abstracted by the study team.
13. Subjects will receive an 8-week supply of test product (BKR-017)
14. Subjects will also be instructed not to make any modifications to their diet or exercise routine.

On Day 0:

1. Day 0 will occur approximately 28 days after the screen visit. The study team will communicate with the subject via a phone call or virtual visit on this day.
2. Study staff will review the subject's diary and CGM data, in order to confirm compliance.
3. Subjects will be questioned about any changes in health status/adverse events and any changes in therapy or medications.
- 4.

